## 9.2 Setting

The setting is any hospital in the countries specified in [Section 9.2.1](#) using any HES product of Fresenius Kabi and willing to document all HES treated patients within the predefined timeframe.

### 9.2.1 Countries, Feasibility and Site Selection

The DUS is intended to be conducted in the following European Member States: Belgium, Czech Republic, France, Germany, Netherlands, Poland, Spain, Sweden, United Kingdom. In order to reduce potential bias from site specific clinical practice it is aimed that per country, at least 5 sites will be included expecting a minimum of about 67 eligible patients per site (depending on the outcome of the feasibility). The sites can only participate upon agreeing to the requested procedures in the participating sites as specified in [Section 9.8.1](#).

Prior to the start of the DUS, a feasibility check/survey will be performed by the CRO to evaluate e.g.

- whether the sites use HES-containing medicinal products from Fresenius Kabi,
- how frequently HES-containing medicinal products from Fresenius Kabi have been used,
- whether the sites use electronic PDMS,
- whether all wards or, if this is not the case, which wards in the hospitals use electronic PDMS,
- which wards have been supplied with HES from Fresenius Kabi within the sites,
- whether the sites collect general consent for using patients' data for research projects,
- whether the sites are willing to participate.

For the retrospective data collection in this DUS, sites using electronic PDMS will be preferred since PDMS allow the comprehensive review of all patient charts at the site regarding administration of HES products in the given retrospective data collection period. Thus, the selection process for sites using HES-containing medicinal products from Fresenius Kabi will be performed following a hierarchic stepwise process as described below:

- (1) HES use and full PDMS coverage within data collection period
- (2) HES use and PDMS use in all wards which have been identified in the survey to be supplied with HES within data collection period
- (3) HES use and PDMS use or paper documentation in all wards which have been identified in the survey to be supplied with HES within data collection period (applies to sites with partial PDMS coverage in HES using wards)
- (4) Sites or wards with HES use within data collection period but paper documentation only

For sites not (completely) using PDMS, the sites' pharmacies will be contacted by the CRO, as part of the feasibility check/survey, to identify the wards which had been supplied with HES from Fresenius Kabi to ensure a high coverage of patients that had received HES. This procedure and the results will be thoroughly documented by the CRO.

After each selection step as described above, identified study sites will be randomly selected per country in case the selection process reveals more than the intended total number of sites.

---

If despite all above mentioned selection strategies the required number of about 334 patients per country cannot be documented within the predefined timeframe, the following measures will be taken in a further hierarchic stepwise manner:

- (A) Extension of timeframe for data collection until November 1st, 2015 (if retrospective nature of the DUS is still ascertained)
- (B) Initiation of new sites in the respective country where 334 patients have not been documented
- (C) Inclusion of additional European countries that have not yet participated and fulfilling the selection criteria (e.g. minimum of 5 centres and sufficient patients)

All new countries and all new sites will be selected according to the feasibility criteria as described above.

All available data, including those from an initially included country where the required patient and/or site number could not be finally achieved, will be analysed in a descriptive manner.

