The retrospective data collection will comprise patient chart data of patients who have been treated between January 1st, 2015 and May 1st, 2015. Patient chart data will be collected going backwards in a predefined timeframe, e.g. of one week (depending on the results of the site feasibility), starting May 1st, 2015 (calendar week 18). All patients treated with HES-containing products of Fresenius Kabi during this week should be documented. In the event that the predefined number of patients per site is not achieved within e.g. this week, data collection can be extended e.g. week by week (again going backwards) until the number of predefined patients has been reached, but not beyond January 1st, 2015. All patients treated with HES-containing products of Fresenius Kabi within the predefined timeframe are documented in the DUS and followed-up until the start and end of HES therapy, even if the start or end of HES therapy are outside the predefined timeframe.

Data collection will include relevant demographic data, main diagnosis at hospital admission, indication for HES use, posology (dosage), and co-morbidities.

The parameters as listed in [Section 9.3](#) will be documented.

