### **9.7.2 Validity of Outcome Measures**

Assessing adherence to the PI specifications in a non-interventional and retrospective DUS will reduce bias to a minimum. In contrast to a prospective setting, the retrospective design of the DUS will not influence the clinical practice but will discover any in-label as well as off-label use.

The inclusion of several countries, study sites and the requirement of inclusion of all identified, HES-treated patients with products of Fresenius Kabi within a predefined timeframe, as well as the dedicated data acquisition in this DUS preferably by electronic PDMS, should provide a comprehensive record of HES-containing medicinal products used in routine clinical practice over all involved investigational sites.

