#### **9.8.1 Procedures in the Participating Sites**

Each site designates one principal investigator for this DUS. He/she will be supported by the appointed CRO and will be responsible for:

- Obtaining local Ethics Committee approval (if required by local requirements) for the conduction of the DUS in his/her site.
- Obtaining a waiver for signed written patient data protection consent if required according to site/national policy.
- Distributing login of the (online) eCRFs together with corresponding training of all site staff involved in the data acquisition.
- Ascertainment of data accuracy, i.e. he/she is responsible for a complete recording of data in the (online) eCRFs in the respective site.
- Notification to the CRO, in advance of data collection and at any time after start of data collection, if the retrospective recording is not or no longer possible or feasible (e.g. due to changes in the resource situation in the participating site).

Depending on national and local requirements, the CRO will facilitate tasks for the principal investigator, e.g. by compiling documents for IEC approval, providing training material and detailed lists of missing or inconclusive data recorded in the eCRF.

Based on local requirements specific training for each site will be provided.

Each participating site will receive an Investigator Site File from the CRO prior to the start of the DUS, containing the following documents:

- DUS protocol
- Short overview of the DUS
- Manual for (online) eCRFs
- Documents for Ethics Committee opinion
- Training slides for investigators and delegated responsible persons
- Login to the eCRFs and an electronic version of all files from the CRO.

To limit bias with regard to possible changes in treatment behaviour concerning the actual use of HES-containing medicinal products, the full set of study documents/information (e.g. all Site Initiation related documents, Trainings, Investigator Site Files) will not be provided to the sites before May 1st, 2015.

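### Fallback (A) extends the treatment window to 1 November 2015, past the date from which sites may hold the study documents, with no cut-off for patients treated after their site received them

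*Protocol*

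**What the plan says.** - **Base window (Protocol 9.1).** "The retrospective data collection will comprise patient chart data of patients who have been treated between January 1" and 1 May 2015. Collection starts at 1 May and works back. If a site is short, "data collection can be extended e.g. week by week (again going backwards) until the number of predefined patients has been reached", with 1 January 2015 as the limit.
- **Safeguard (Protocol 9.8.1).** The stated aim is this: "To limit bias with regard to possible changes in treatment behaviour concerning the actual use of HES-containing medicinal products". For that reason the complete study documentation, including training, "will not be provided to the sites before May 1", 2015. The same section has each site receive its Investigator Site File before the study starts there.
- **Fallback (Protocol 9.2.1).** The trigger is that "the required number of about 334 patients per country cannot be documented within the predefined timeframe". Three remedies then apply in a fixed order. The first, labelled (A), is "Extension of timeframe for data collection until November 1" 2015. Next come (B), new sites in that country, and (C), further countries. (A) is conditional on the study still being retrospective. The condition is not defined further.
- **Validity claim (Protocol 9.7.2).** "In contrast to a prospective setting, the retrospective design of the DUS will not influence the clinical practice".

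**The concern.** The outcome is physicians' adherence to the revised product information. By withholding documents, the sponsor accepts that prescribers who know their HES use will be reviewed may change it. In the base window the safeguard works by date: the documents cannot reach a site before the window closes. Fallback (A) is the only provision that moves the window forward, and nothing moves the safeguard with it.

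A patient added under (A) may therefore have been treated by staff who already held the protocol or had been trained on the adherence criteria. If that improves prescribing, measured non-compliance falls. This would happen only in countries that missed their target, and a confidence interval would not show it. Section 9.7.2 would not hold for these patients, and the limitations in Section 9.9 do not mention the issue.

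**Working it through.** **1. The plan's own figures.** Table 1 (Section 9.5) uses the exact binomial interval. With x = round(334 × 0.03) = 10, the 95% interval is 1.4% to 5.4%. With x = round(3000 × 0.03) = 90, it is 2.4% to 3.7%. Both match, as do all 32 cells of the table. Precision is not in dispute.

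**2. Calendar arithmetic** (dates from Sections 9.1, 9.2.1 and 9.8.1).
- Base window, 1 January to 1 May 2015: 120 days.
- Extension, 1 May to 1 November 2015: 184 days.
- Extended window: 120 + 184 = 304 days.
- Share after the earliest permitted release: 184/304 = 60.5%.

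**3. Is 1 November a treatment date or a chart-extraction deadline?** The milestones in Section 6 use the term data collection for chart extraction, so the wording of (A) is loose. Extraction starts about 3 to 4 months after PRAC approval and the related notifications, and ends 9 to 12 months after that. Assume approval no earlier than the protocol's version date, 7 May 2015. The earliest start is then 7 August to 7 September 2015, and the end lies between May and September 2016. A deadline of 1 November 2015 would shorten extraction, not extend it. Only the treatment-window reading fits.

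**4. How much of the extension must follow receipt of the site file?** The file arrives before the study starts at the site, so it is in hand by the start of extraction. On the assumption in step 3:
- start 7 August: 86 days remain to 1 November (86/304 = 28% of the extended window);
- start 7 September: 55 days remain (55/304 = 18%).

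Later approval shortens this stretch. It disappears if extraction starts after 1 November. Earlier release, permitted from 1 May, lengthens the exposed period, up to the full 184 days.

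**5. Does the condition on (A) close the gap?** Take a patient treated in October 2015 at a site trained in September, with the chart read in December. The chart review is retrospective, so the condition as worded is met, yet the prescriber could have known of the study. The condition concerns when charts are read. The safeguard concerns what the prescriber knew.

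**6. Illustration of size (all inputs assumed except N = 334 and the 3% rate, which is the protocol's example).** Let f be the share of a country's patients treated after awareness and r the factor by which awareness multiplies non-compliance. The expected estimate is 3% × (1 − f + r·f).

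| f | r | Expected estimate |
|---|---|---|
| 0.10 | 0.75 | 3% × 0.975 = 2.9% |
| 0.50 | 0.50 | 3% × 0.750 = 2.25% |
| 0.60 | 0.25 | 3% × 0.550 = 1.65% |

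The documents give no value for f or r.

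**The case against.** **The condition can be read more broadly.** Section 9.7.2 ties the retrospective design to having no influence on practice, so the condition on (A) might be meant to bar patients treated under awareness of the study. If it said so, the gap would largely close. But it gives no test, date or responsible party, and its plain sense is met by the October example above.

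**1 May is a floor, not a release date.** This stands. A reader might infer that 61% of the extended window, or of its patients, is unprotected. The documents support only an upper bound in calendar time. Site selection and contracting follow approval (Section 9.1), and actual release dates are not given.

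**The base window is not perfectly blind either.** This also stands. Only the full set of documents is withheld. Sites are surveyed beforehand on HES use and willingness to take part (Section 9.2.1), and Annex 1 lists a participating-site list dated 4 May 2015. A cut-off at first contact of any kind would therefore be too strict and could remove base-window patients.

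**New sites should not automatically come first.** A reader might conclude that (B) must precede (A). That is a trade-off: sites are chosen in order of electronic record coverage, so added sites may come from lower tiers. Nor can extension back before 1 January 2015 be recommended from the documents, which do not say when the revised product information took effect in each country.

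**The study is descriptive.** Section 9.7.1 plans separate country estimates and no formal comparisons, so a claim of invalid country comparisons would go too far. The country estimates themselves could still be biased.

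**Conclusion.** The inconsistency stands on the protocol's own dates. The safeguard ends on 1 May 2015, the first fallback adds 184 days after it, and the condition on (A) does not exclude patients treated once their site held the documents or had been trained.

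The consequence is limited and contingent. It arises only if (A) is invoked and only for patients treated after their site received the material. A reader might infer that the safeguard as a whole is defeated. The documents do not support that, because the withheld documents cannot reach sites before the base window closes.

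The exposed period is at most 184 of 304 days (61%). At the earliest timing, 55 to 86 days certainly follow receipt of the site file, assuming approval no earlier than 7 May 2015 and extraction 3 to 4 months later. Upward bias in adherence is the expected direction if awareness improves prescribing. Its size is unknown, and the range of 2.9% to 1.65% against a true 3% is illustrative only.

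**What to change.** Amend (A) in Section 9.2.1 in one of two ways:

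- limit it to patients whose HES treatment started before their site received the documents or training withheld under Section 9.8.1, with that date logged by the CRO for each site; or
- keep this material from a site until its extended window has closed. This works only where the extension is decided before the site is initiated.

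In either case, flag any patient treated after the site's date, report these patients separately, and leave them out of the main adherence estimate. Word the cut-off as receipt of the withheld documents or training, so that the feasibility survey does not trigger it. Limit the statement in Section 9.7.2 to patients treated before that date.

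The cost is one logged date per site and possibly fewer patients from (A), so step (B) may be needed sooner. Admission week and year are already recorded (Section 9.3.2), which allows an approximate flag. For patients admitted close to the cut-off, the site would need to confirm whether HES started before or after it.

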### **9.2.2 Source Population**

The source population includes all patients fulfilling the inclusion ([see Section 9.2.3](#)) and none of the exclusion criteria ([see Section 9.2.4](#)).

In the context of this DUS, the inclusion and exclusion criteria are minimised to obtain a representative overview of the routine use of HES in clinical practice.

The retrospective review of patient data in the identified sites will start about 3 to 4 months after protocol approval by the PRAC, final site selection and notification to NCAs and positive IEC opinion as required by national and local regulations and requirements.

### **9.2.3 Inclusion Criteria**

- Patients who were receiving any of the HES-containing medicinal products listed in Annex 1a within the predefined timeframe will be documented in the DUS.

### **9.2.4 Exclusion Criteria**

- Patients who were included in interventional clinical trials treating patients with HES-containing products within the predefined timeframe.

*Patients who were treated with HES within an interventional clinical trial are excluded since a clinical trial protocol may require study specific use outside clinical routine practice.*

### 9.3 Variables

#### 9.3.1 HES Usage in the Hospital

Data on the “HES usage in the hospital” are documented in an eCRF and will be used for assessing the coverage of patients that had received HES products of Fresenius Kabi (see [Section 9.2.1](#)).

The parameters regarding the HES usage of Fresenius Kabi will be assessed as follows:

- Hospital
  - Name
  - Address
  
- Estimated average HES amount used per week in:
  - Hospital (total amount in study site)
  - Intensive Care Unit (ICU) (if various, specify)
  - Paediatric Intensive Care Unit (PICU)
  - Operating room
  - Surgical ward
  - Intermediate care
  - Emergency unit
  - Burns unit
  - Other (please specify)

Data on the estimated use of HES products of Fresenius Kabi will be based on the supplied amount of HES as reported by the hospital pharmacy or hospital’s HES supplier.

#### 9.3.2 Anonymised Patient Specific Variables

Below listed parameters are documented in the eCRF. A high validity and accurateness of these parameters is expected as their documentation is part of clinical routine and they are essential for therapeutic decisions and reimbursement.

To evaluate the effectiveness of risk minimisation measures via assessing the adherence of hospital physicians to the revised European PI of HES-containing medicinal products concerning indication, posology (dosage) and contraindications, various parameters will be assessed. These are as follows:

##### **Basic Assessment**

- Hospital (name, address)
  
- Patient admission date (calendar week, year)

- Ward(s) where HES of Fresenius Kabi was administered
  - ICU (if various, specify)/PICU/Operating room/Surgical ward/Intermediate care/Emergency unit/Burns unit/Other
- Demographic data
  - Age (< 18 years or ≥ 18 years)
  - Weight
- Main diagnosis at hospital admission (ICD-10 code plus corresponding plain diagnosis text)
- Indication for HES use
  - Treatment of Hypovolaemia due to acute blood loss (yes/no)
  - Treatment of Hypovolaemia without acute blood loss (yes/no)
  - HES used exclusively for “Prophylaxis of Hypovolaemia” and not for “Treatment of Hypovolaemia” (yes/no)
  - Other (yes/no; if yes ICD-10 code)

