##### **Rationale and Background**

The European Medicines Agency (EMA) Pharmacovigilance Risk Assessment Committee (PRAC) recommended in the Article 107i procedure according to Directive 2001/83/EC for HES-containing medicinal products (EMA/H/A-107i/1376) in October 2013 that HES solutions must no longer be used to treat patients with sepsis or burn injuries or critically ill patients because of an increased risk of kidney injury and mortality while the benefit-risk ratio for HES-containing medicinal products remains favourable in the treatment of hypovolaemia due to acute blood loss when crystalloids alone are not considered sufficient.

The final implementing decision, issued by the European Commission (EC) on December 19, 2013, implicates new contraindications, new special warnings and precautions for use as well as other changes to the European Product Information (PI) [Summary of Product Characteristics (SmPCs); Package Leaflet] for risk minimisation measures (as requested in Annex III of this EC decision).

To “evaluate the effectiveness of the risk minimisation measures taken” (as requested in Annex IV of the EC decision), the concerned MAHs of HES products subject to the PRAC procedure were asked to conduct a Drug Utilisation Study (DUS) with HES-containing medicinal products in several European Union (EU) Member States.

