## **9. Research Methods**

### **9.1 Study Design**

The study is a retrospective, non-interventional, multinational, multi-centre European DUS of use of HES-containing medicinal products in hospitals. The DUS will follow national laws and regulations.

Outcome measure is the adherence to the concerned sections of the revised European PI for HES-containing medicinal products.

Usage of these medicinal products according to indications, posology (dosage), and contraindications as specified in the revised PI of the HES solutions will be assessed.

In the DUS, routine clinical use of HES-containing medicinal products of Fresenius Kabi will be documented by retrospective data collection from patient charts within a predefined timeframe. Retrospective data collection best reflects actual patterns of use and allows reducing bias as described in [Section 9.9](#) to a minimum. To ensure that there is a very high coverage of patients administered HES containing products, site selection will focus on sites using electronic PDMS. Patient charts will be thoroughly searched via free text, ICD-10 code (diagnosis), and ATC code (medication) to ensure identification of eligible patients as complete as possible.

Following the final approval of the submitted protocol by the PRAC, notification to NCAs and positive IEC opinion as required by national and local regulations and requirements, as well as the administrative processes such as site selection and contracting of sites will be initiated.

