#### **Relevant Co-Morbidities Before HES Administration**

Operational definitions for the below listed variables (co-morbidities) are given in Annex 5, apply for this DUS only and must be considered when the information for the respective variable is to be entered in the eCRF from patient charts.

- Hypersensitivity to HES or to any of the other excipients in the HES product (yes/no)
- Burns (yes/no)
- Disturbed fluid status (yes/no)
  - Dehydration (yes/no)
  - Hyperhydration (yes/no)
- Severe hyperkalaemia (yes/no)
- Severe hypernatraemia (yes/no)
- Severe hyperchloraemia (yes/no)
- Congestive heart failure (yes/no; if yes: NYHA stage)
- Pulmonary oedema (yes/no)
- Severely impaired hepatic function (yes/no)
- Renal failure
  - Renal impairment (yes/no)
  - Renal replacement therapy (yes/no)

- Severe coagulopathy (yes/no)
- Systemic inflammation
  - Sepsis (yes/no)
  - Severe sepsis (yes/no)
  - Septic shock (yes/no)
- Clinically relevant intracranial/cerebral bleeding (yes/no)
- Organ transplant patient (yes/no)
  - Acute organ transplant patient (yes/no)
  - Date of transplantation, if available (calendar week, year)

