## 9.4 Data Sources

Data entry based on patient charts, preferably from electronic PDMS, will be performed by the investigators or delegated responsible persons at the participating site using the online eCRFs.

The eCRFs will be structured according to the parameters described in [Section 9.3](#).

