### **9.9 Limitations of the Research Methods**

The following types of bias or limitations may occur in this retrospective, non-interventional DUS:

- The retrospective design may lead to an underestimation of amounts of HES products of Fresenius Kabi given due to incomplete data documentation.
- Source data verification of the data by the CRO by reviewing the individual patients' original medical records will not be possible.
- There is a certain unavoidable bias possible due to the hospital selection strategy.

- The total amount of sites having electronic PDMS implemented or having PDMS only partially implemented may affect the study timelines. In particular low PDMS coverage in sites might negatively impact the study timelines.

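### Adherence on indication rests on undefined yes/no items whose charted basis is not captured and which omit the crystalloid condition

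*Protocol*

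**What the plan says.** Section 9.1 sets the outcome: "Usage of these medicinal products according to indications, posology (dosage), and contraindications as specified in the revised PI of the HES solutions will be assessed". The abstract's rationale, and Section 7 in nearly the same terms, describe the use with a favourable benefit-risk ratio as "treatment of hypovolaemia due to acute blood loss when crystalloids alone are not considered sufficient".

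Under Basic Assessment in Section 9.3.2, indication is recorded by four yes/no items. The first is "Treatment of Hypovolaemia due to acute blood loss (yes/no" and the second is "Treatment of Hypovolaemia without acute blood loss (yes/no". The third covers purely prophylactic use. The fourth is a category for other uses, and only this one asks for an ICD-10 code.

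For the co-morbidities the protocol goes further: "Operational definitions for the below listed variables (co-morbidities) are given in Annex 5". The title of Annex 5 in the table of contents confines it to co-morbidities.

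Section 9.4 says that data entry "will be performed by the investigators or delegated responsible persons at the participating site using the online eCRFs". Section 9.9 concedes: "Source data verification of the data by the CRO by reviewing the individual patients' original medical records will not be possible". Section 9.3.2 nevertheless states: "A high validity and accurateness of these parameters is expected as their documentation is part of clinical routine".

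**The concern.** The study judges whether hospital physicians kept to the label. On indication, staff at the same hospital make that judgement at abstraction. They hold the protocol (it is in the Investigator Site File, Section 9.8.1) and therefore know what is being assessed. Sorting a case into hypovolaemia with or without acute blood loss is a study classification. It is not a value that can simply be read off every chart.

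If a chart gives no clear reason for HES, the abstractor must choose an answer or leave a blank, and the edit checks will query the blank. The facts behind the choice never reach the database, so the analysis plan cannot reconstruct them. Sites could then differ in reported adherence because they abstract differently, not because they prescribe differently. A large sample would give such a figure a narrow interval without making it more accurate.

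**Working it through.** **1. How the protocol treats its other variables (Section 9.3.2)**

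- Posology: start, end and volume are recorded for each bag, so dose adherence can be derived from recorded facts.
- Co-morbidities: yes/no items, with operational definitions that abstractors must apply.
- HES before admission: yes, no, or an explicit answer for absent information.
- Indication: yes/no items with no definition, no answer for absent information and no supporting field. The variable list contains no blood loss, bleeding event, crystalloid use or charted reason for HES.

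**2. The item against the indication**

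As the protocol reports it, the indication has two parts: acute blood loss, and crystalloids alone judged insufficient. The item covers the first part only, and no other field covers the second. If a yes is counted as adherent, a patient who meets the first part but not the second is counted as adherent. Taken alone, this omission can only raise apparent adherence. The documents give no basis for its size.

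**3. The protocol's own precision figures (Section 9.5, Table 1)**

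The method is the exact binomial 95 % interval, as stated there, at a rate of 3 %.

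- N = 334: 334 × 0.03 = 10.02, so x = 10, giving 1.44 to 5.44 %. Table 1 has 1.4 to 5.4 %.
- N = 3000: x = 90, giving 2.42 to 3.67 %. Table 1 has 2.4 to 3.7 %.

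Both reproduce. These intervals reflect sampling error only.

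**4. Illustration of misclassification**

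Let p be the true off-label share on indication, f the share of off-label uses ticked on-label, and g the share of on-label uses ticked off-label.

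Reported rate = p(1 − f) + (1 − p)g

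The value p = 3 % borrows the protocol's example, which concerns non-compliance in general. The values of f and g are assumptions. With g = 0 and N = 3000:

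- f = 10 %: 3000 × 0.027 = 81, or 2.7 % (95 % CI 2.15 to 3.34 %), which includes 3 %.
- f = 25 %: 3000 × 0.0225 = 67.5, so x = 68, or 2.27 % (1.76 to 2.86 %), which excludes 3 %.
- f = 50 %: 3000 × 0.015 = 45, or 1.5 % (1.1 to 2.0 %), which excludes 3 %.

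With f = 25 % and N = 334: 334 × 0.0225 = 7.5, so x = 8, or 2.4 % (1.04 to 4.66 %), which includes 3 %. The expected shift, 3 % × 0.25 = 0.75 percentage points, is the same at both sample sizes. Only the interval narrows.

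**5. Direction**

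The shift cancels when (1 − p)g = pf, that is g = pf/(1 − p).

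- f = 25 %: 0.0075/0.97 = 0.77 %.
- f = 50 %: 0.015/0.97 = 1.55 %.

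A small rate of opposite errors is therefore enough to offset the bias, so arithmetic alone does not fix the net direction.

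**The case against.** A reader might infer that on-label use will be over-reported. The documents do not support that certainty. They give no error rate and state no incentive. Three of the four indication items are off-label, one of them dedicated to prophylaxis, and step 5 shows how few opposite errors would cancel the shift. What stands is that over-reporting is possible and the likelier direction.

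A reader might also infer that the answer has no charted evidence behind it. That is wrong: Section 9.4 and the abstract say entry is from patient charts. What is missing is capture of that evidence in the eCRF.

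Nor is the item wholly uncheckable. Admission diagnosis, ward and co-morbidities allow a coarse consistency check, and Section 9.8.2 provides plausibility queries and data formats suitable for audit. These checks are weak, because site staff answer the queries and the stored data contain the tick without its basis.

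The protocol discloses the lack of source verification itself, so that is no hidden defect. However, Section 9.9 does not name indication misclassification. Finally, the eCRF manual, the training slides and the content of Annex 5 are not shown, and the manual may define the items. A definition there would help consistency between sites, but it would not add the missing facts to the database. Withholding study documents until 1 May 2015 protects prescribing behaviour, not later abstraction.

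**Conclusion.** The point holds in limited form. One of the three adherence outcomes rests on items with no definition in the protocol, no answer for a silent chart, no recorded basis and no verification against source. The on-label item omits half of the indication as the protocol states it, so a correct yes is not sufficient for on-label use.

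The resulting error cannot be quantified from the data to be collected, and 3000 patients do not reduce it. The figure of about 2.3 % (1.8 to 2.9 %) against a true 3 % is an illustration. It rests on an assumed 25 % one-way error and on applying the general 3 % example to indication. At an assumed 10 %, the pooled interval still covers 3 %. The likelier direction, towards adherent, is a judgement based on who abstracts the data and on the omitted condition. It is not a result from the documents. This is an inexpensive improvement to a main outcome, and it has to be made before abstraction starts.

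**What to change.** Add to the indication block in Section 9.3.2:

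- (a) the reason for HES as charted at the time of administration, or 'no reason charted';
- (b) whether acute bleeding is charted before or during the HES infusion, with the blood loss or bleeding diagnosis as recorded;
- (c) whether the chart records that crystalloids alone were considered insufficient (yes / no / not documented).

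Keep the site's yes/no items and tabulate them against (a) to (c). In Section 9.7.1, report 'indication not documented' as its own category, and show adherence on indication twice, counting those patients once as adherent and once as non-adherent. In Section 9.9, list indication misclassification as a limitation. Qualify the expectation of high validity in Section 9.3.2 so that it does not extend to the indication items without support.

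The cost is a few more eCRF fields taken from a chart that is already open. Abstraction takes slightly longer, especially at paper-only sites, which Section 9.2.1 allows, and the report will show a visible 'not documented' group. The same staff still enter the data, so this makes the basis of each answer visible but does not replace verification.
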